5.2.2 Secondary objectives

For the secondary objectives the participants will include all people presenting to ZTBI YY community TB case finding services in Sleman district and Yogyakarta City who screen positive for TB.

Inclusion Criteria:

- Adults and adolescents 12 years old and above (including pregnant women)
- Able and willing to consent. For adolescents aged 12-17, verbal consent as well as parental/guardian informed consent will be required

Exclusion criteria:

- Unable to provide sputum
- Currently receiving anti-TB therapy
- Patients who are seriously ill and need to be admitted to hospital
- Patients with potential COVID-19 referred for further assessment

'hotspot' sites for screening are identified based on TB program records of previously reported TB cases within the preceding 3 years. Designated sites for screening are identified more than 2 weeks in advance to allow time to notify relevant authorities and the community near the intended screening site of the service and the free access to screening for TB, with community mobilisation by trained community cadres in consultation with the Dinas Kesehatan. Screening consists of symptom screening and CXR with computer aided diagnosis (CAD) software reading of CXR using qXR software. Those who screen positive based on symptoms or abnormal CXR (qXR interpretation) during screening have a spot sputum collected for molecular testing.

Household contacts of microbiologically confirmed cases are screened for symptoms and with tuberculin skin testing and also referred for CXR by mobile screening or at the nearest CXR facility. Household contacts who screen positive based on symptoms or CXR will have a spot sputum sample collected for molecular testing.

5.4 Study Procedures

5.4.1 Objective 1

1a. Adequacy of Truenat training as measured by post-training assessment

Laboratory staff from UGM with experience in performance of rapid molecular diagnostic testing for TB will be identified and trained as an onsite trainer and observer and certified by Molbio staff for this purpose. A total of 8 non-laboratory staff as well as 2 laboratory staff will be trained in the use of Truenat. Training will be delivered using a training package of presentations and video materials. The training will also include hands-on training with the Truenat devices using de-identified sputum remnants with known geneXpert results. These sputum remnants will be provided by the UGM laboratory. Staff trained to use Truenat will include ZTB YY active case finding laboratory staff and health care workers who will be involved in delivering TB active case finding in Sleman and Yogyakarta City using Truenat; as well as Universitas Gadjah Mada laboratory staff; and selected health facility staff from government health facilities in Sleman and Yogyakarta City.

All individuals who are trained will be invited in person by a member of the study team to be participants under objective 1a at the start of the training, will be provided with the PICF and will have until the end of the training to consider participation.

Training proficiency assessment components will include:

- i. Observation of 'hands-on' operation of test and software using an observation checklist (see appendix 5). This will be carried out in-person by a qualified trainer. The trainer will then observe the user perform the test and score the trainee's proficiency against each of the key criteria in the checklist. Proficiency testing will be conducted for all users directly after the initial training is delivered, and then again 1 month into the intervention period. Users will need to achieve a fully correct score on proficiency testing before they are approved to operate the test in routine practice and must repeat the training and test until they obtain an adequate proficiency score. In the case of repeat testing at baseline (immediately after the initial training), only the first test done by a user will be included in the baseline analysis.
- An assessment of user understanding of Truenat testing fundamentals and troubleshooting actions. Shortly after conducting the observation checklist described above, the trainer will administer a questionnaire to the user to assess understanding of key aspects of the training (see Appendix 6).

The capability of laboratory and non-laboratory personnel to proficiently operate the test will be determined by calculating the proportion of users who meet performance targets after initial training.

1b Operational performance of Truenat as measured by platform failure rates and error rates

The logs from each device will be extracted by a member of the study team without patient identifying information. This data will be analysed to determine the number of tests performed, platform failures, errors and indeterminate results. In addition, electronic records will be maintained by laboratory staff conducting Truenat testing on the number of tests done, results and retests required, as well as logs of any outage time and the reason (e.g. device failure, battery depletion). Truenat operational performance will then be assessed using:

- Truenat platform failure rates (the proportion of total working hours that the platform failed to be operational due to any reason). This will be calculated as total platform failure rate using the amount of time that assays cannot be performed due to a failure of one or more of the Truenat devices.
- ii. Truenat error rates (the proportion of tests with an error result, disaggregated by error type).

1c Instrument User and health service provider views regarding feasibility and acceptability of decentralised Truenat

Views on the acceptability and operational challenges of Truenat will be assessed by a survey of laboratory staff and healthcare workers (HCWs) within the program. The survey will be divided into two sections with one section to be completed by HCW if they perform the Truenat test; and the second section to be completed by staff who are involved in registering, interviewing and assessing screening participants. Staff who work in the provision of mobile active case finding services that include Truenat testing in Sleman and Yogyakarta City will be invited, as well as lab staff who perform the Truenat tests and health facility staff at facilities where patients tested with Truenat are diagnosed and started on treatment. These staff will be contacted with an invitation to participate via Whatsapp or email. The invitation will provide a summary of the study and the purpose of the survey, as well as a unique survey link which will ensure that each staff member can only complete the survey once. The survey link will direct potential participants to a REDCap survey with an electronic PICF as the initial page. The potential participant must complete the consent form electronically with a signature before they can access the anonymous survey. The survey will be made live for one month and participants can exit the survey without consenting and later return to complete the consent process at any time during that month if they wish to participate. The survey will assess general satisfaction, ease of use, confidence in the results compared with standard of care, and problems/challenges to active case finding of use of Truenat (including HCW perception of acceptability to patients) and will include structured questions as well as open-ended questions.

1d Screening participant views regarding acceptability of point-of-care Truenat performed within mobile active TB case finding service

Views of study participants will be obtained regarding the acceptability of point-of-care Truenat through individual in-depth qualitative interviews. Purposive sampling will be used to include a diversity of sex, age, whether tested microbiological positive or negative and household contacts and community participants. Interviews will be administered 1-7 days after the initial screening. Interviews will be conducted by a researcher experienced in qualitative interviewing who is separate from the active case finding/screening team. Selection of individuals to approach will be done by the researcher working with the database manager to find people enrolled within the preceding 3 days matching specified criteria. The researcher will contact the participant by telephone, with a maximum of up to 3 phone attempts. If the participant answers the call, the reason for the call will be explained and the person will be invited to participate in a telephone

interview with an explanation that this will take up to 45 minutes either to be done at this time or at a time within the next 3 days convenient to the participant.

A telephone interview will be used as this is deemed to be less time consuming and is easier for people with the ongoing impact of COVID-19 on travel movement in Yogyakarta. Verbal informed consent will be obtained. The interview guide is outlined in Appendix 7. The person will be asked whether the interview can be recorded. If the participant agrees the call will be recorded and transcribed after which the call recording will be deleted. If the participant does not agree to call-recording the interviewer will take notes. The transcription and/or notes will have a unique identifier that is not the participants name, along with age and sex recorded. No other potentially identifying information will be recorded. As compensation for time spent contributing to the study via the interview, at the end of the interview, participants will be sent an electronic phone credit voucher to their phone number.

5.4.2 Objectives 2 and 3

Baseline Visit

Participants attending the TB active case finding service who screen positive for potential TB by symptoms or chest X-ray will be invited to participate in the study. A study team member will explain the participant information and consent form (PICF) in person and participants who consent to participate will sign and date the PICF. For participants who are illiterate, thumbprint, witness signature and date will be recorded on the PICF. Persons who do not consent to participate in the study will receive standard of care diagnosis (submit a single sputum specimen for central GeneXpert laboratory testing) and their results will not be included in the study. Potential participants have the time between the initial invitation to participate and the cessation of TB screening by the mobile active case finding service on that day to decide whether they wish to participate.

Data on study enrolment will be entered into a study-specific enrolment instrument in the ZTB YY active case finding REDCap database. The instrument will record the person's patient ID as well as their study ID and the details of their consent.

A nurse will discuss with the participant the potential that they have TB and that they require further testing for TB. They will have the process for sputum sample collection explained and spot sputum samples will be collected under observation following a standard approach for ensuring good quality sputum collection and infection control. Depending on the diagnostic

LOCATE TB Research Protocol v1.1 (2022-08-25)

strategy assigned for the particular screening day the participant will receive either standard of care or decentralised Truenat testing:

- For standard of care participant samples will be sent to a centralised laboratory for GeneXpert testing. The participant will be informed that they will be notified of their results when they become available in 1-3 days. Those with GeneXpert MTB positive results will be informed by telephone to attend the nearest puskesmas for counselling and commencement of TB treatment. Those testing GeneXpert negative for MTB will have their case reviewed by the doctor at the health facility for their catchment to determine if they need further follow up or not in accordance with the standard ACF protocols.
- For decentralised **Truenat**, two spot sputum samples will be collected and the participant will be informed that their sample will be tested on the day, and will be asked if they prefer to wait for the result or be contacted when the result is available.
 - Where a patient has a positive result on Truenat MTB Plus, the Truenat MTB-RIF Dx assay will be performed to test for rifampicin resistance. Patients with a positive result on Truenat MTB Plus will be informed of the result and advised to attend the nearest puskesmas or hospital for counselling and commencement of TB treatment, or referral to another facility of their choice for treatment.
 - Those testing negative for MTB will have their case reviewed by a doctor at the catchment health facility to determine if they need further follow up in accordance with the standard ACF protocols; and taking into consideration the result of the GeneXpert MTB/RIF assay
 - Due to National Tuberculosis Program requirements all patients tested with Truenat will also be tested with GeneXpert MTB/RIF using the second spot sputum sample. Treatment will be initiated based on positive Truenat or GeneXpert Mtb/RIF result, with review by the TB active case finding service doctor of cases where the result is discordant.
 - Commencement of TB treatment will be according to standard national TB protocols. Further clinical care and diagnostic investigations will be provided within governmental health care services. If a patient wishes to seek further care at a specific health facility or service of their choosing they will be provided with a referral.

The testing and treatment algorithm for patients in the Truenat Arm

Follow-Up Interview

Participants will be called at a 14-day phone visit (+/- 7 days). Three attempts will be made to contact a participant by phone. In the event that the participant is still not contacted, a phone call to the agreed trusted contact will be made to find out about the participant's whereabouts and to ask if they can arrange for the participant to return a call or to be visited at an acceptable time. A home visit will be conducted for those participants who cannot be reached by phone or who identify that they prefer a home visit or do not have access to a phone.

The phone visit or in person home visit will repeat the symptom screening questions, as well as ask about whether TB was diagnosed, how TB was diagnosed, when the participant was informed about the TB results, if and when the participant attended the health care service (Puskesmas, private or other) and if TB treatment had been commenced.

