5.7 Outcome Measures

Primary Endpoint

- 1. The operational feasibility of point-of-care Truenat, which will be assessed by:
 - a. Adequacy of Truenat training as measured by post-training assessment
 - b. Operational performance of Truenat as measured by platform failure rates and error rates
 - c. Instrument User and health service provider views regarding feasibility and acceptability of Truenat.
 - d. Screening participant views regarding acceptability of point-of-care Truenat performed within mobile active TB case finding service

Secondary endpoints

- Median time from sample collection to result for Truenat compared to centralised GeneXpert Mtb/RIF
- The median time from sample collection to treatment initiation for Truenat compared to centralised GeneXpert Mtb/RIF

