5.10 Statistical methods and data analysis

Data endpoints for quantitative analyses and the means of calculating the proportions are summarised in table 1. For objectives 2 and 3 endpoints will be compared between Truenat and standard of care.

Cleaning and analysis of quantitative data will be conducted using R (The R Project for Statistical Computing, v4.1.2). QSR nVIVO will be used to support the coding and analysis of qualitative data.

5.10.1 Objective 1

Objective 1a

Proficiency in performing testing using Truenat Mtb Plus and MTB-RIF Dx will be assessed for all persons who undertake the training. The proportion of users who were proficient in their first post-training test will be calculated. Score summaries will be analysed as descriptive data. Among those who did not pass their first post-training, proportions will be calculated for failure for each of the competencies in the checklist. The median number and range for the number of repeat tests until proficient will be calculated for those who fail their first test.

Objective 1b

Descriptive statistics will be calculated for the number and proportion of hours that the platform was unavailable due to failure, with further disaggregation of failure by the reason for the failure. Descriptive statistics will also be calculated for the proportion of assays with an error, with disaggregation by error type.

Objective 1c

Survey data from closed-ended user feasibility and acceptability survey questions will be analysed to produce contingency tables and plots of the data, while open-ended survey questions will be coded and analysed qualitatively using a thematic approach.

Objective 1d

Patient in-depth semi-structured interviews will be analysed thematically: transcripts will be translated from Indonesian and coded using previously identified thematic codes from survey and interview guide development as well as codes that emerge during analysis. All coding will be done by at least two researchers, aiming for independent review followed by consensus through

LOCATE TB Research Protocol v1.1 (2022-08-25)

discussion. Themes and findings will be analysed both separately (users, HCWs and patients) and combined as a means of cross verification. QSR NVivo will be used to support the coding and analysis of qualitative data.

5.10.2 Objectives 2 and 3:

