 - Did you observe problems during the screening days when Truenat was used? If "yes", what problems did you observe?
 - Did you observe problems during the screening days when GeneXpert testing at another laboratory was used? If "yes", what problems did you observe?
 - Do you have a preference for which test you would prefer to offer within the mobile screening service? If "yes", why?

11 Appendix 2. User Feasability and Acceptability Survey Part 2 – Ease of Use

To be filled by each Laboratory technician, Nurse, Doctor, who has performed the Truenat Mtb Plus and MTB-RIF Dx tests. Please complete the following sections on

Have you performed testing with Truenat Mtb Plus and MTB-RIF Dx prior to this? Yes No

Please tick applicable: Number of Truenat tests performed: <20 tests >20 tests

Actual number of tests done if less than 20 (estimate):

Please comment on how you found performing each of the following activities.

Question 1: Was the activity difficult, OR easy?

Question 2: Do you have any comment?

Item	Answer 1: Difficult = D; Easy = E;	Answer 2: Comments
Understanding the Truenat Mtb Plus test information leaflet		
Turning on the True prep Auto device		
Preparing and adding sample to Trueprep cartridge and loading in Trueprep Auto device		
Removing Eluate from Trueprep cartridge and		
Transferring required amount of eluate by pipette to Truenat Mtb Plus chip		
Turning on the Truenat Mtb Plus Truelab micro PCR Analyzer		
Turning on and connecting the mobile device		
Entering patient ID and sample details		

Item	Answer 1: Difficult = D; Easy = E;	Answer 2: Comments
Loading chip and commencing Truelab Dx micro PCR Analyzer machine		
Reading the results		
Printing the results		
Interpretation of the result as either positive or negative for MTB		
Loading MTB-RIF Dx chip		
Interpretation of the result as positive or negative for rifampicin resistance		
Retest instructions		
Disposal of the cartridges and chips		
Disposal of the pipette		

If you were training someone on performing the Truenat test:

What are the most important things you would teach them?

If you were training someone on Reading the Truenat Results:

What are the most important things you would teach them?

General comments

- At which steps of the Truenat testing procedure do you think there may be risks of errors?
- After how many tests did you feel fully comfortable with the whole procedure (i.e. you were able to perform all steps without any hesitation)?

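### The printed 1c staff survey has no item on confidence in Truenat against GeneXpert results or on staff-perceived patient acceptability, and no direct satisfaction item, although Protocol 5.4.1 says it measures all three

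*Protocol*

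**What the plan says.** Component (c) of the primary endpoint in Protocol 5.7 is "Instrument User and health service provider views regarding feasibility and acceptability of Truenat". Section 5.4.1 (1c) describes the survey that supplies it: "The survey will assess general satisfaction, ease of use, confidence in the results compared with standard of care", and then "problems/challenges to active case finding of use of Truenat (including HCW perception of acceptability to patients". It adds that the survey "will include structured questions as well as open-ended questions".

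The survey has two sections, one for staff who perform the test and one for staff who register, interview and assess people at screening. Section 5.8.2 uses branching to route respondents. The question text is in Appendix 1 (1A for performers, 1B for staff in the diagnostic process) and Appendix 2 (ease of use, performers only).

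On analysis, 5.10.1 states: "Survey data from closed-ended user feasibility and acceptability survey questions will be analysed to produce contingency tables and plots of the data". Open answers are to be coded thematically. Section 5.9.1 expects 10-15 respondents. The survey is open for one month, is anonymous, and can be completed only once per person.

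**The concern.** The description in 5.4.1 and the printed questions do not match. Some of what 5.4.1 says will be assessed has no question behind it.

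This matters because 1c is part of the primary endpoint. The mixed-methods part of 5.10 gives each type of analysis equal weight in testing the proposition that laboratory staff, non-laboratory staff and the community accept Truenat well. Section 5.10.1 also plans to set the themes from users, health workers and patients against each other as a cross-check.

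Confidence in results is not a side issue. Under 5.4.2 every Truenat-arm participant is also tested on GeneXpert, and discordant results go to a doctor for review. Staff may therefore see the two tests disagree, yet the survey does not ask which result they trust. Because answers are anonymous and given once, a respondent's missing answers cannot be collected later.

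**Working it through.** No figure is involved. The check sets the content promised in 5.4.1 against the questions in Appendices 1A, 1B and 2.

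**Domain 1, general satisfaction.** No question asks for it directly and none rates it. The nearest items are open: in 1A, views on introducing Truenat (with benefits and challenges) and on workload; in Appendix 2, perceived advantages and main challenges. All of these go to performers. In 1B the only near-substitute is "Do you have a preference for which test you would prefer to offer within the mobile screening service". As laid out, it sits under the heading for staff who report results back to participants, so some 1B respondents may not see it. Result: indirect only.

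**Domain 2, ease of use.** Covered by an open question in 1A and by the Appendix 2 grid, which asks "Question 1: Was the activity difficult, OR easy" for 17 printed rows. Both are for performers. Result: covered.

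**Domain 3, confidence in results compared with standard of care.** No item in any section. Two come close. Appendix 2 asks at which steps errors might arise, but makes no comparison with GeneXpert. The 1B preference item is comparative, but a preference may rest on speed or workload and need not reflect trust in the result. Result: no item.

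**Domain 4, problems and challenges.** Covered by questions on challenges, delays, sample transport, and problems seen on Truenat days and on GeneXpert days. Result: covered in the main.

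**Named sub-part of domain 4, acceptability to patients as staff see it.** The patient-related questions concern producing sputum, delays, the information given, and explaining results. None asks how patients received on-site testing. Result: no item.

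**Count.** Of four listed domains, 2 are covered in the main (ease of use; problems and challenges), 1 is covered only indirectly (satisfaction) and 1 has no item (confidence): 2 + 1 + 1 = 4. In addition, the one sub-part named within domain 4 has no item.

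**By branch.** Performers have the Difficult/Easy grid and several open questions on general views. The 1B section has no rating grid. Its closed content is a few yes/no questions on problems and preference, so for staff who complete only 1B the closed-item tables in 5.10.1 have little to draw on.

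**The case against.** The strongest reply is that the plan can still report acceptability. Endpoint 1c is about views, and 5.10.1 provides thematic analysis of open answers. Views on introduction, benefits, workload and preferred test are usable for that. Section 5.10.1 promises tables only for whatever closed questions exist; it does not promise one per domain or per role. Patients' own views are collected first-hand in the 1d interviews. Section 1B also holds open questions on turnaround, delay and explaining results. Finally, 5.4.1 does not cite Appendices 1 and 2 for 1c, whereas it cites the appendices for 1a and 1d, and 5.8.2 says the REDCap survey is still to be set up, so the final form could differ.

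Much of this stands. A reader might infer that three of the four domains have no items. The documents do not support that: patient acceptability is a parenthetical part of the fourth domain, which is otherwise covered, and satisfaction is reached indirectly. A reader might also infer that staff acceptability cannot be reported at all. That goes too far, for the reasons just given. The absence of a rating scale is not in itself an error.

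The mismatch remains all the same. The 1d interviews give patients' views, while 5.4.1 separately promises the staff's perception of them, and the planned cross-check needs both. Thematic coding can pick up confidence or patient acceptability only if a respondent happens to raise it. As for completeness, the appendix titles identify this survey and nothing marks the text as an excerpt.

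**Conclusion.** The point holds in a limited form. Two topics that 5.4.1 says the survey will assess have no question: confidence in Truenat against GeneXpert results, and staff-perceived acceptability to patients. A third, general satisfaction, has no direct question and is close to unmeasured for staff who do not run the test. Administered as printed, these parts of 1c could not be reported as planned or taken into the triangulation for any of the 10-15 expected respondents. Ease of use, challenges and general views could.

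This rests on Appendices 1 and 2 being the whole survey. It is not a matter to leave to a statistical analysis plan, since the description and the questions are both in the protocol. It is worth correcting before launch, but it does not undermine the primary endpoint as a whole.

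**What to change.** Before the survey goes live:

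- Add to both branches one short closed item, with an optional comment, on each of: overall satisfaction with on-site Truenat testing; confidence in Truenat results compared with GeneXpert; and perceived acceptability of on-site testing to participants.
- Put the existing preference question to all respondents.
- List these items in 5.10.1 as the 1c acceptability measures, tabulated by role.

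Keep the procedural questions in Appendix 1 (storage, disposal, reading time), because they bear on feasibility. If a separate item on confidence in the rifampicin result is wanted, put it only to staff who perform the test or handle that result.

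The cost is three added items, one moved item and one sentence in 5.10.1: a slightly longer survey, with no extra participants. The alternative is to amend 5.4.1 so that it describes only what the appendices ask. That restores consistency but gives up the missing topics.
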